### **Statistical methods planned, including handling data exclusion, analysis of sub-groups if any**

Any patient that did not conclude all three treatments shall be excluded from the analysis. If there are fewer than 37 patients remaining after the study concludes and exclusions are applied, than no analysis shall take place and additional study subject enrolled until a minimum of 40 completed participants exist. In the event that a patient concludes at least one treatment session, but afterwards discontinues

participation in the study, the presence of the patient in the study shall be acknowledged for data analysis purposes. Missing data for such acknowledged participants shall be fulfilled by inserting the least favorable result obtained realized from among all test subjects who did complete the study. Statistical analysis shall then proceed on the fully populated study data.

Primary analysis shall consist of applying the Anova single-factor acceptance test evaluating the change in waist circumference based on the data collected by the tape measure. A confidence of  $P=0.05$  shall be applied. The results of this data shall be directly applied to determining if the primary objective of the study has been met.

A correlation analysis shall be applied to all variable data recorded, as well as key calculations from the data, to identify any potential two-way connections or relationships between sets of data. Any correlations scoring a magnitude of 0.85 or greater shall be discussed and if appropriate, Anova single-factor analysis applied to determine if there is statistical significance to the relationship and any statements that might be supported by the data. Of primary interest is any impact the starting BMI might have on the amount of change, and any impact that gender may impart to the outcome.

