## **Statistical Methods**

Single factor ANOVA analysis will be used to determine if the extent of circumference reduction in the test group is statistically significant over changes in the control group. Additional correlation assessment will be performed to identify any potential relationships between patient data sets, and single-factor ANOVA assessment applied to those correlations as applicable. Missing or incomplete data shall be populated using least-favorable data from participants who did complete the study.

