## DATA ANALYSIS

### **Data quality assurance**

Patient and study data will be documented on physical, printed patient treatment session sheets. The completed sheets will be provided to the sponsor, who has the responsibility of uploading the data into electronic files for statistical analysis and processing. Calculations made from the data will be conducted in the electronic files, and the accuracy of calculations provided by the electronic spreadsheets shall be relied on. The clinicians and those who participate in the data collection will not have access to the electronic files, calculations, or analyses. Electronic data management tools are also employed to perform the statistical analysis of the key data.

Accuracy of the measurements made by the tape measure are verified by the sponsor. This is confirming the calibration status of the device via the manufacturer's certificate of calibration, as well as verification by measuring rigid metal cylinders with the device and comparing the measurements with NIST traceable calibrated calipers to measure the sample diameter from which the circumference can be calculated.

Where patients discontinue participation in the study, or key data is not documented properly on the treatment sheets, data from such patients shall not be incorporated in the statistical analysis of the data.

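### Patients who stop after one or two sessions are both excluded from the analysis and kept with an imputed value, and no text settles which rule governs the primary analysis

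*Combined protocol and SAP*

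**What the plan says.** Four pieces of text bear on a patient without complete data.

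- The section on planned statistical methods (under Data Analysis) begins: "Any patient that did not conclude all three treatments shall be excluded from the analysis".
- The same section then sets a completer count, "If there are fewer than 37 patients remaining after the study concludes and exclusions are applied", below which no analysis is done and enrolment continues until 40 have completed. It goes on: "In the event that a patient concludes at least one treatment session, but afterwards discontinues", the patient is still acknowledged for data analysis, and missing data are filled by "inserting the least favorable result obtained realized from among all test subjects who did complete the study". It ends this part with "Statistical analysis shall then proceed on the fully populated study data".
- Data quality assurance covers patients who discontinue, "or key data is not documented properly on the treatment sheets", and states that "data from such patients shall not be incorporated in the statistical analysis of the data".
- The Synopsis, under Statistical Methods, gives only the imputation rule: "Missing or incomplete data shall be populated using least-favorable data from participants who did complete the study".

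The paragraph that defines the primary ANOVA names no analysis population. Both eligibility lists also include non-completion as an exclusion criterion.

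**The concern.** Excluding a patient and imputing that patient's result are different analyses of the same trial. The primary objective asks for a reduction of at least 1 inch and for statistical significance, and the two rules can place the result on different sides of either requirement. The sponsor enters the data and performs the analysis. The planned independent review can confirm the calculations, but it has no single prespecified rule to check them against. Attrition is expected: the Sample size section recruits 50 partly to allow for it, and the analysis may go ahead with 37 completers.

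A second gap follows if there are two arms. The title page and Synopsis describe a test and a control group, whereas Study configuration describes a single arm. With two arms, the least favorable result could mean the smallest reduction for everyone, or the value that most hurts the device in each arm. The plan does not say which.

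**Working it through.** **The rules side by side**

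| Patient | Planned methods, opening sentence | Data quality assurance | Planned methods, later sentences, and Synopsis |
|---|---|---|---|
| Stops after one or two sessions | Excluded | Data barred | Kept and imputed |
| Three sessions, then discontinues with no week-12 measurement | Not covered | Data barred | Kept and imputed |
| Key data badly documented | Not covered | Data barred | Populated, if this counts as missing or incomplete |

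The first row is a direct contradiction inside one section. The other two rows depend on how Data quality assurance is read (see the objection).

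**The plan's own figure.** Sample size inputs: 1.96, 0.84, SD 1.50 inches, d = 1.0 inch. n = 2 × (1.96 + 0.84)² × 1.5² / 1.0² = 35.28, which rounds up to 36. The plan states 37, and a t-based version gives 36.3, rounded up to 37. The figure reproduces closely enough. Only the SD and the completer counts are used below.

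**Illustration, single group.** From the plan: SD 1.5, 40 completers, 50 recruited, 1-inch threshold. Assumed: 10 dropouts who resemble completers, the threshold applied to the group mean, the true mean, and the distribution. The imputed value is the smallest reduction among the 40 completers.

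Imputed group mean = (40 × completer mean + 10 × worst completer value) / 50.

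- Normal data, true mean 1.0: the expected worst value is −2.24, a waist gain. (40 × 1.00 + 10 × (−2.24)) / 50 = 0.35 inch, against 1.00 under exclusion.
- Gamma data (never negative), mean 1.0, SD 1.5: the expected worst value is about 0.00. (40 × 1.00 + 0) / 50 = 0.80 inch.
- Normal data, true mean 1.5: under exclusion the standard error is 1.5/√40 = 0.237, so the chance of a mean of at least 1 is Φ(0.5/0.237) = 98%. Under imputation the expected worst value is −1.74 and the expected mean is (60 − 17.4)/50 = 0.85. The simulated chance of reaching 1 inch is 30%.
- Gamma data, mean 1.5, SD 1.5: 99% under exclusion. Under imputation the expected worst value is 1.5/40 = 0.0375 and the expected mean is (60 + 0.375)/50 = 1.21. The chance is 86.5%.

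**Illustration, two arms.** Assumed: 25 per arm, normal data, SD 1.5, no true effect, 2 test and 8 placebo dropouts, and the smallest reduction among all completers given to dropouts in both arms. With both true means 0, the expected worst of 40 completers is −3.24. The test mean becomes 2 × (−3.24)/25 = −0.26 and the placebo mean 8 × (−3.24)/25 = −1.04, a spurious 0.78 inch in the device's favor. Simulated results (40,000 replicates, two-sided 0.05):

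- Device-favoring ANOVA error is about 25%, against about 2.5% under exclusion. Taking each arm's own minimum also gives about 25%.
- Also requiring a test-arm mean of at least 1 inch, it is about 0% if both true means are 0. If both are 1, it is 11% (pooled minimum) to 13% (own-arm minimum), against about 2.4% under exclusion.
- With the split reversed (8 test, 2 placebo), the error of about 25% goes against the device.
- If dropouts instead receive the value least favorable to the device in each arm, device-favoring error is about 0% and error against the device is about 59%.

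**The case against.** The best defense is that the section gives an order: apply exclusions, check the count of 37, acknowledge anyone with at least one session, impute, then analyze. On that reading exclusion serves only the count and imputation governs, which agrees with the Synopsis. Data quality assurance can also be reconciled. It bars a patient's own data, and an imputed value comes from a completer. Nor is improper documentation plainly the same as missing or incomplete data.

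Much of this stands. A reader might infer that the primary analysis cannot be carried out at all as written; the documents do not support that, because the sequencing sentence points to one workable reading. The conflict is sharpest for patients with one or two sessions, and weaker for the other two kinds of patient.

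The defense does not close the matter. The opening sentence excludes patients from the analysis, not from a count. Data quality assurance mentions no count and makes no exception. The primary-analysis paragraph is silent on who is in it. Limiting imputation to patients who finished all three sessions does not work either, because the rule expressly starts at one session.

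The size is also open to challenge. The 30% figure depends on a normal lower tail in which the worst completer gains waist. The Sample size section speaks of people who may not respond at all, which is closer to no change, and the gamma result is then much milder. Finally, the objectives do not say that the inch refers to the group mean.

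**Conclusion.** The conflict is real. For a patient who stops after one or two sessions, the plan gives two opposite instructions. The text leans towards imputation without settling it, so the rule could be chosen after data are seen.

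In the single-group illustration the imputed mean cannot exceed the completers-only mean, so the direction is fixed while the size is not. At a true mean of 1.5 inches with 10 of 50 imputed, the chance of reaching 1 inch falls from 98–99% to somewhere between about 30% (normal) and 86.5% (gamma). At a true mean of 1.0 inch, the expected mean falls from 1.00 to between 0.35 and 0.80. A reader might infer that imputation would sink a successful device; that depends on dropout numbers and a distribution that the documents do not give.

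With two arms, the rule is not always conservative, because uneven dropout can move the ANOVA either way. The 25% error should not be read as the trial's false-success rate. It needs the assumed 2/8 split and leaves out the 1-inch requirement, with which it becomes about 0% or 11–13%, depending on the true means. Nothing in the documents suggests an intention to choose the rule after the fact; the point is only that the wording would allow it.

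**What to change.** Before data are seen:

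- Name one primary analysis set: all patients who start treatment or, if there are two arms, all randomized patients as assigned.
- Name one primary missing-data rule, and make the Synopsis, Data quality assurance and the section on planned statistical methods agree with it.
- Treat improperly documented values as missing under that rule.
- If the least-favorable value is kept, define it by arm.
- Report the completers-only analysis as a sensitivity analysis.
- State that the 37/40 trigger in the Synopsis (Recruitment) and in the planned methods is a recruitment count that removes no one from the analysis.
- Remove non-completion from both eligibility lists, since it cannot be judged at entry and works as a further exclusion of dropouts.

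The first two items cure the contradiction. A model-based method that uses waist readings already collected is an option, not a requirement. The cost is wording changes and a little more analysis work, with no new visits or measurements.

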## **STUDY OBJECTIVES**

**PRIMARY** - The primary objective of this study is to determine if the application of lower frequency (35kHz to 45kHz) ultrasound energy to the waist/abdominal region of the human body is capable of effecting a reduction in the amount of subcutaneous adipose cells and/or tissue to an amount of at least 1 inch and to a statistically significant level. Determination of the reduction in this adipose tissue is achieved via measurement of the body circumference that includes the abdominal area that was treated, and comparing measurements prior to the initial treatment with measurements after the entire treatment regime is concluded. Per the proposed clinical mechanism of action, the disrupted tissue is cleared by the lymphatic system which facilitates excretion or elimination of the disrupted tissue contents. Having been eliminated, the patient should exhibit a reduction in waist circumference. For this objective to be successfully achieved, a reduction in waist circumference of at least one inch must be demonstrated at a point of 12 weeks after the last of three treatment sessions has been applied.

**SECONDARY** - The secondary objective of this study is to assess the safety of this device. Assessment is made by having the patient rate the treatment experience and report any symptoms, side effects, or associated abnormal conditions. Additional assessment is made by the investigators to qualitatively confirm if visually detectable abnormal conditions (example: edema) are presented following the treatment. Success is determined by whether the patients indicate that any discomfort experienced during the treatment, and following the treatment that are directly attributable to the treatment, along with an absence of side-effects or abnormal conditions directly attributable to the treatment, create a risk/benefit condition where the benefit of treatment is regarded to outweigh the risks and temporary discomfort. Quantitatively, the benefit is regarded to outweigh the risk when: 1) No patients report a pain rating of 4 or higher on the Stanford Pain Scale, 2) No patients exhibit any side effects or abnormal conditions at the conclusion of the final treatment, and 3) No patient who was included in the Test group reports that the treatment regimen was unsuccessful.

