#### TREATMENT (total time of activity, 14-18 weeks - 4-6 weeks for the 1st, 2nd, and 3rd treatment applications, and 12-14 weeks following the 3rd treatment for follow-up visit):

##### Individual Treatment Session (approximately 70 minutes)

###### Prior to the Treatment (about 10 minutes):

- The patient is scheduled to arrive at the study site to undergo a treatment.
- The date of the treatment and the time of arrival will be documented in the treatment session record.
- During the first treatment only: The patient is given the Q-Pre Survey to fill out.
- The assigned pre-treatment investigator measures the waist circumference of the patient and documents this in the Pre-Treatment record, with these measurements being made by the blinded assessment clinician as described in the Measurement Tools and Methods section of this protocol.
- Prior to Treatments 2 and 3, the patient will be asked for the study diary, and the pre-treatment investigator shall review the diary and the patient's previous post-treatment Anticipated Effects and Adverse Event forms and discusses with the patient the items that are recorded about any abnormal body functions or observations that may be relevant to the treatment. If any are indicated, these will be documented in the patient record. Additional record shall be made by the investigator as to whether past events and observations have been resolved or are still unresolved.
- The patient is moved to the treatment area.

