- Possible increased compromise of immuno-suppressed patients: Patients who are or have recently experienced systemic procedures or conditions that weaken or suppress the immune system may be further weakened as a result of this treatment, as the process is expected to utilize immune responses to clear away the treated sub-cutaneous tissues.

If any adverse events occur, such will be immediately reported to the principal investigator who will assess the events and make determinations about whether the study should be halted or modified, or whether the participant should be excluded from further participation in the study. The study sponsor shall also be notified of the adverse event and of the principal investigator's assessment and decision regarding any action towards the participant or the study.

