### **Sample size**

A total sample size of a minimum of 40 patients was established for this study. This number is based on

$$n = \frac{2 \cdot (Z_\alpha + Z_\beta)^2 \cdot \sigma^2}{d^2}$$

where:

$Z_\alpha = 1.96$ , based on a confidence of  $P=0.05$  (false rejecting of a true null hypothesis),  
 $Z_\beta = 0.84$ , based on a power of 80% (failure to reject a false null hypothesis),  
 $d = 1.0$  inch reduction in waist circumference as a meaningful/successful change in measurement,  
 $\sigma = 1.50$  inches, based on the evidence presented by a published study under similar treatment parameters and conditions reporting a typical response of 0.75 inches through the umbilical region and assuming some of the population may not respond at all.

The resulting calculation gives a population size of 37. Accounting for possible attrition and adding a generous margin of safety, a recruitment size of 50 individuals is arrived at. Review of the data analysis shall be conducted by an independent entity to confirm the handling and calculation of data, and the conclusions drawn from the data regarding statistical significance.

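### The plan does not separate stopping treatment from leaving the study, and makes no provision to collect and use the week-12 waist of a patient who stops sessions early

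*Combined protocol and SAP*

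**What the plan says.** The combined protocol and SAP gives two rules for a patient who does not finish the three sessions.

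- **Exclusion.** Statistical methods planned opens with: "Any patient that did not conclude all three treatments shall be excluded from the analysis". Data quality assurance says of patients who discontinue, or whose key data are poorly documented, that "data from such patients shall not be incorporated in the statistical analysis of the data". Both eligibility lists (synopsis and main text) also name non-completion as an exclusion criterion.
- **Filling in.** Later in Statistical methods planned, for a patient who has at least one session and then discontinues participation, "the presence of the patient in the study shall be acknowledged for data analysis purposes". Missing data are supplied by "inserting the least favorable result obtained realized from among all test subjects who did complete the study". The synopsis section Statistical Methods gives only this rule.

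The timing of the endpoint visit is worded in two ways. Study Objectives sets it "12 weeks after the last of three treatment sessions has been applied", and the Treatment section allows "12-14 weeks following the 3rd treatment for follow-up visit". The synopsis Methodology, the Introduction, Sequence and duration of study period, and Follow-up count from the last or final treatment instead.

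After an adverse event, Adverse Interactions has the principal investigator decide whether to halt or modify the study, or "whether the participant should be excluded from further participation in the study". It does not mention ending sessions while staying in follow-up.

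**The concern.** A patient may stop sessions and still be willing to have a waist measurement at week 12. The plan has no status for this patient. Under the exclusion rule the reading is not used even if someone takes it. Under the filling-in rule a patient who discontinues receives another patient's worst result, and nothing arranges for that patient's own value to be obtained.

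Primary data that could have been observed are therefore lost, in a group selected by what happened during treatment. Success is judged against a fixed 1-inch threshold, so a modest shift in the mean matters. A missed visit cannot be recovered at the analysis stage. Choosing between the two rules would not cure this, because neither provides for the patient's own measurement.

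**Working it through.** **Inputs from the plan.** About 50 recruited, with at least 40 completing (Recruitment); no analysis below 37 (Statistical methods planned); SD 1.50 inches, d = 1.0 inch, calculated n = 37 (Sample size); success at 1 inch or more at week 12 (Study Objectives).

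**The plan's own figure.** 2 × (1.96 + 0.84)² × 1.5² / 1² = 35.28, or 36 after rounding up. The two-sample t version gives 36.3, hence 37, so the stated figure reproduces. The margin up to 50 allows a loss of (50 − 40)/50 = 20% or (50 − 37)/50 = 26%.

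**Assumptions not in the plan.** The treated group's mean change is compared with 1 inch, as in a single-arm reading; data are normal with SD 1.5; completers average 1.0 inch; the stoppers' mean is varied.

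**Exclusion rule.** Error of the completer-only mean = stop fraction × (completer mean − stopper mean).
- 10 of 50 stop, stopper mean 0: all-treated mean (40 × 1.0 + 10 × 0)/50 = 0.80; error 0.20 × 1.0 = +0.20.
- 13 of 50 stop, stopper mean 0: (37 × 1.0 + 13 × 0)/50 = 0.74; error +0.26.

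**Filling-in rule.** By simulation, the expected lowest result among 40 completers is about −2.24 inches (a gain in waist). The filled-in mean is (40 × 1.0 + 10 × (−2.24))/50 = 0.35.

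With 40 completers and 10 stoppers:

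| True stopper mean (inch) | All-treated mean | Error, exclusion | Error, filling in |
|---|---|---|---|
| 0 | 0.80 | +0.20 | −0.45 |
| 0.5 | 0.90 | +0.10 | −0.55 |
| 1.0 | 1.00 | 0 | −0.65 |
| 1.5 | 1.10 | −0.10 | −0.75 |

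With only 5 stoppers of 50 and a stopper mean of 0, the errors are +0.10 and −0.23.

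**Chance that the analysed mean reaches 1 inch** (simulation; completer mean 1.25, stopper mean 0, SD 1.5):

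| Completers / stoppers | Completers only | All observed week-12 values | Filling in |
|---|---|---|---|
| 40 / 10 | 85% | 50% | 7% |
| 45 / 5 | 87% | 72% | 36% |

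Under these assumptions the handling of stoppers can decide the result.

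**The case against.** A reader might infer that the plan is a completer-only analysis biased toward the device. The documents do not support that. The filling-in rule stands in the same section and alone in the synopsis, and in the table it errs against the device. A bias in the device's favor needs both the exclusion rule and stoppers who do worse.

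A reader might also infer that stoppers will be the non-responders, because Sample size speaks of "assuming some of the population may not respond at all". That phrase supports the choice of SD and says nothing about who stops. At gaps of 6 to 8 days, three sessions span only about two weeks. If stoppers do as well as completers, the exclusion error is zero; if they do better, it reverses.

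Nor can one say that stoppers have no week-12 visit, or that it is already paid for. Last or final treatment can mean the last session received. The Introduction plans three follow-up visits per patient. Data Analysis and Final Reports waits for every participant who can be reached and is willing. The text is ambiguous rather than silent, and no budget appears. Adverse Interactions also leaves room for other action toward the participant.

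The filling-in rule addresses missing data for those who discontinue participation, so by its words it would not overwrite a reading actually taken. The exclusion sentence is what discards it.

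Finally, the primary objective is worded for the full three-session regimen, so an all-treated estimate answers a somewhat different question. That is a fair defense of keeping a completer analysis, but not of leaving willing patients unmeasured.

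These objections limit the direction and size of the claim. They do not supply the missing provision.

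**Conclusion.** The point holds in this form: the plan does not distinguish stopping treatment from leaving the study, and neither of its rules provides for collecting and using a stopper's own week-12 waist. The direction of the resulting error is not fixed. The exclusion rule can overstate waist loss if stoppers do worse than completers; least-favorable filling can understate it.

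The figures of 0.80 and 0.74 against a completer mean of 1.0 are a worst case. They assign the entire attrition margin to treatment stoppers with no change at all. That margin also covers losses after the third session and refusals of follow-up, which this change could not recover, and Sample size describes it as generous. The completer and stopper means, the normal data and the number of stoppers are assumptions; the documents report no outcome by completion status. The change should be made before enrolment, because it concerns data collection.

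**What to change.** Amend Treatment, Follow-up, Adverse Interactions and Statistical methods planned. To avoid new contradictions, bring both eligibility lists, Study Objectives and Data quality assurance into line:

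1. Define stopping treatment and withdrawing from follow-up as separate events, and record the reason for stopping.
2. Ask patients who stop sessions to attend the planned follow-up visits, at minimum for the 12-week waist, timed from the last session received.
3. Make the primary analysis include everyone treated at least once, using observed week-12 values whether or not three sessions were given. Keep the three-session completer analysis as supportive.
4. Apply the missing-data rule only where week 12 is truly unobserved, and remove the exclusion sentences that conflict with this.

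Decisions to stop treatment stay with the investigator.

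The cost is protocol and consent wording, plus up to three follow-up visits of about 15 minutes per stopper, of a kind already planned. The estimate may be smaller than a completer-only one, or larger than one based on least-favorable filling.

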## **Inclusion/Exclusion Criteria**

Inclusion in the study consists of the following criteria:

- Age equal to or above 18.
- Body Mass Index  $\geq 25$ .

Exclusion from the study consists of the following criteria:

- Age equal to or below 17.
- Body Mass Index  $< 25$ .
- Open sores, wounds, or otherwise compromised skin in the treatment area
- History of keloid formation, hypertrophic scarring, or abnormal/delayed wound healing.
- Known or suspected pregnancy, or active nursing.
- General systemic conditions of arteriosclerosis, anemia, aortic aneurysm, or hypertension.
- Liver conditions such as hyperlipidemia, hepatitis, liver disease, or abnormal liver function
- Diabetes or blood-glucose sensitivity
- Any prior invasive cosmetic surgery to the waist or abdominal area, such as liposuction.
- Hernias or diastasis recti within the treatment area.
- Concurrent, or within the last 6 months, participation in any clinical trial for another device or drug.
- Existing bacterial or viral infections (influenza, rhinovirus, hepatitis, pneumonia, tuberculosis, and the like)
- Presence of acne vulgaris, herpes zoster, psoriasis vulgaris, or similar skin conditions in the treatment area.
- Any type of cosmetic treatment to the target area within the last 6 months.
- Implanted active medical device anywhere in the subject, or metallic or polymeric implants in the vicinity of the treatment area.
- Currently undergoing, or recently underwent, chemotherapy or radiation treatment.
- Per the investigator's discretion, any physical or mental condition which may compromise the patient's safety or welfare.
- Failure to complete the study as outlined.

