## **Recruitment**

Recruiting shall consist of about 50 patients, with a target of at least 40 patients completing the study. Should patients drop out of the protocol such that 37 patients are not achieved at the end of the study, additional patients shall be recruited to achieve the target number.

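### The rules for patients who stop early contradict each other and are not confined to the waist endpoint, so on one reading patients who stop because of harm leave the safety judgement

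*Combined protocol and SAP*

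**What the plan says.** **Rules that exclude.** Under Data quality assurance, for patients who discontinue or whose key data are badly documented, "data from such patients shall not be incorporated in the statistical analysis of the data". The statistical methods section of Data Analysis opens with "Any patient that did not conclude all three treatments shall be excluded from the analysis". The Inclusion/Exclusion Criteria list "Failure to complete the study as outlined" as an exclusion. None of these asks why the patient stopped.

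**Rules that retain.** Later sentences of the same statistical methods section keep a patient who had one or more sessions and then left, and fill that patient's missing data with the worst result seen among completers. The Synopsis (Statistical Methods) has a similar rule for filling missing data.

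**The floor.** "If there are fewer than 37 patients remaining after the study concludes and exclusions are applied, than no analysis shall take place", with "additional study subject enrolled until a minimum of 40 completed participants exist". The Synopsis (Recruitment) likewise says that below 37 "additional patients shall be recruited to achieve the target number".

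**Safety.** The secondary objective in Study Objectives is met on three conditions: no pain rating of 4 or more, "No patients exhibit any side effects or abnormal conditions at the conclusion of the final treatment", and no Test-group patient reporting that the regimen failed. After an adverse event, the Adverse Interactions section has the principal investigator decide, among other things, "whether the participant should be excluded from further participation in the study".

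**Reach of the analysis rules.** The Introduction says that the data analysis determines success on both the primary and the secondary objectives. Data Analysis and Final Reports sends the study data through the Data Analysis section. No safety analysis population is defined.

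**The concern.** Stopping because of pain or an adverse event is among the most informative safety outcomes in a device trial. The plan provides two routes to it: a patient may halt a session for discomfort (Application of the Treatment), and the principal investigator may remove a patient after an adverse event. A rule that excludes patients without regard to reason, and is not limited to efficacy data, can take these patients out of the safety result.

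The safety conditions are absolute: each requires that no patient has the event. One omitted patient can therefore turn a failed safety objective into a met one. The reader of the final report would have no required table from which to see that this had happened.

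**Working it through.** **1. The plan's own figure.** Inputs from Sample size: Z values 1.96 and 0.84, standard deviation 1.50 inches, difference 1.0 inch.

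2 × (1.96 + 0.84)² × 1.50² / 1.0² = 2 × 7.84 × 2.25 = 35.28, which rounds up to 36.

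A t-based version of the same two-group calculation gives exactly 37 per group, so the stated 37 is reproduced to within one patient. It matters here only as the floor for analysis.

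**2. Room above the floor.** Recruitment is 50 (Sample size).

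- 50 − 37 = 13, and 13/50 = 26%. Up to 13 patients can be removed and the analysis still proceeds.
- The 14th loss (14/50 = 28%) defers analysis and reopens enrolment to 40 completers.

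The plan states no dropout rate, so the chance of 14 or more losses among 50 is shown for assumed rates (binomial tail):

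| Assumed dropout rate | Chance of 14 or more of 50 |
|---|---|
| 10% | 0.03% |
| 20% | 11.1% |
| 30% | 67.2% |

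Re-enrolment needs heavy dropout. Removal of some patients without breaching the floor is the likelier route to bias.

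**3. What happens to a patient who stops after session 1 or 2.**

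| Safety condition | Exclusion rules | Retention rules |
|---|---|---|
| 1. Pain rating | Ratings already recorded leave the analysis | Recorded ratings stay and count; only missing ones are filled |
| 2. Side effects at the final treatment | Patient not in the analysis | Never observed; filled with the worst completer result |
| 3. Regimen reported unsuccessful | Patient not in the analysis | Q-Post Survey not given: in the treatment phase it is issued only at the final session, and follow-up surveys are timed from the final treatment |

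Take a patient who rates pain 7 at session 1 and withdraws. Under retention, condition 1 fails. Under exclusion, that rating is not counted. For condition 2, if every completer is free of side effects, the worst completer result is itself no side effect, so imputation records the early stopper as event-free. It can never show harm worse than a completer had.

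**4. How easily the choice of rule matters.** The plan gives no rate of stopping for harm, so rates are assumed. The chance that none of 50 treated patients stops for harm is (1 − rate)^50: 36.4% at 2%, 7.7% at 5% and 0.5% at 10%. Even at low rates, at least one such patient is likely.

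**5. Extreme illustration.** Suppose that all 13 removable patients stopped for harm: 13/50 = 26%, exact 95% interval 14.6% to 40.3%. If the remaining 37 were event-free, the exclusion reading would report 0/37, with a two-sided upper limit of 1 − 0.025^(1/37) = 9.5%. This shows what the rules permit. It is not a forecast.

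**The case against.** The strongest reply is that nothing in the plan says safety is judged on completers. The pain condition refers to patients without qualification. The only analyses specified are a waist ANOVA and a correlation analysis, whereas the safety conditions are simple counts, so the exclusions can be read as applying to the waist and correlation data alone. Pain, anticipated effects and adverse events are recorded after every session (Post-Treatment Assessment), and the retention rule fills only missing data, so a recorded high pain score would still count. The principal investigator assesses each adverse event as it is reported and may halt or modify the study, and the sponsor is told (Adverse Interactions). Record review and a full third-party audit of adverse effects cover everyone (Monitoring).

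Most of this stands, and it rules out stronger readings that a reader might infer:

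- *That the plan limits safety to those who tolerated the device.* No section says so. It is one possible result of unreconciled rules.
- *That each harmed patient is dropped and replaced.* Replacement starts only when fewer than 37 remain; it is not one for one.
- *That heavy dropout suppresses the analysis, or exposes more people with no safety review.* Analysis is deferred to 40 completers, and review of individual events continues. What is missing is a required cumulative table.

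The reply does not remove the defect. The Introduction and Data Analysis and Final Reports put the safety objective through the section that contains the exclusions, and nothing there exempts safety data. The retention rule does not help with conditions 2 and 3, for which an early stopper has no observation.

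**Conclusion.** The concern holds in this form. The rules on discontinued patients contradict each other, none is limited to the waist endpoint, and no safety population is defined. On the exclusion reading, patients who stop because of pain or an adverse event leave the safety judgement. On either reading, they are not observed for the side-effect condition at the final treatment and are not given the Q-Post Survey.

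Up to 13 of 50 patients (26%) could be removed before the floor is reached. How many of those would be harm-related cannot be known from the documents; all 13 is an assumed extreme. The conclusion does not depend on that figure, because with absolute safety conditions a single omitted patient can change the result. This is more than missing detail, since the rules followed as written permit it. It also assumes that the final treatment means the third session, which is how the treatment sequence reads.

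**What to change.** 1. Reconcile the Synopsis (Statistical Methods), Data quality assurance and the statistical methods section so that they give one rule for discontinued patients.
2. State that the exclusion, imputation and no-analysis rules apply to the waist endpoint only.
3. Define a safety set of every patient who received any part of one session. Assess the three conditions in Study Objectives on that set, using all recorded pain ratings, anticipated effects and adverse events, without imputation. Read condition 2 at each patient's last treatment received.
4. Report discontinuations by reason beside the safety result, whether or not 37 patients remain, and produce that table with the cumulative safety data before any further enrolment under the floor rule.
5. Report withdrawal for pain separately. Making it an automatic failure would add an endpoint beyond the stated pain threshold, and this point does not call for that.

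The cost is a few sentences in the Synopsis, Study Objectives and Data Analysis, and one table from data already collected. The downside is that the safety result may look less favourable.
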